The trial aims to evaluate the impact of a one-off classroom-level information and engagement session conducted by a 'lay' counsellor as compared to school-level sensitization activities on the demand for school counselling program among adolescents in government-run secondary schools in New Delhi, India. This trial is part of a larger research program called PRIDE (PRemlum for aDolEscents) whose overall goal is to develop and evaluate a trans-diagnostic, stepped-care intervention targeting common mental disorders in school-going adolescents in India. The PRIDE intervention architecture involves two sequential psychological treatments of incremental intensity. The first step is a brief problem-solving intervention delivered by lay counsellors. Adolescents with enduring mental health problems are referred to a higher intensity trans-diagnostic treatment delivered by psychologists. The trial described here is embedded within a trial testing the effectiveness of the low-intensity problem-solving intervention (host trial). The trial protocols for both these trials are elaborated in a journal publication(1). The trial is registered prospectively on ClinicalTrials.gov/ct2/show/NCT03633916 (available at: https://clinicaltrials.gov/ct2/show/NCT03633916).

3. Objectives and Hypothesis

The primary objective of this stepped-wedge, cluster randomised controlled trial is to evaluate the impact of a classroom sensitization session (intervention condition), over and above school-level sensitization activities (control condition), on the rate of referred adolescents (i.e. the proportion of adolescents referred as a function of the total sampling frame in each condition) into the host trial.

The secondary objectives are:

- To evaluate the proportion of such referrals meeting the eligibility criteria of the host trial across the control and intervention conditions
- To evaluate the proportion of such referrals that are self-referrals across the control and intervention conditions
- To explore the severity of mental health symptoms reported by referred adolescents across the control and intervention conditions
- To explore the symptom sub-types (internalising and externalising symptoms) reported by referred adolescents across the control and intervention conditions

The primary hypothesis is that the classroom-level sensitization intervention will be associated with a higher referral rate into the host trial, compared with referrals arising from school-level sensitization activities in isolation.

The secondary hypotheses are:

- Compared with the control condition, the intervention condition will be associated with a greater proportion of referred students who meet eligibility criteria for inclusion in the host trial.
- Compared with the control condition, the intervention condition will be associated with a greater proportion of students who self-refer.
- Compared with the control condition, the intervention condition will be associated with adolescents reporting a greater severity of total symptoms experienced and a greater severity of internalising and externalising symptom types.

Outcome	Outcome Explanation						
PRIMARY OUTC							
Referral rate into the host trial	The referral rate will be calculated as the number of referred students from a given condition divided by the total number of students in corresponding classes. This will be calculated from researchers' referral logs. Referrals will be recorded continuously and reported for each 4 weeks' time period, for the total study duration of 12 weeks. It will be entered as a binomial variable at the student level indicating if student was referred during the trial	Referral logs					
SECONDARY OU	TCOMES						
Eligibility rate	Eligibility rate is defined as the proportion of referred participants meeting eligibility criteria for the host trial, as a function of the number of referred adolescents in a given condition. Host trial eligibility criteria are as follows: (i) Total Difficulties score on the adolescent-reported Strengths and Difficulties Questionnaire (SDQ) >/= 19 for boys & >/= 20 for girls (2); (ii) SDQ Impact Supplement score of >/=2; and (iii) chronicity of mental health problems for >/= 1 month. Referred students will complete the SDQ as part of the host trial's screening assessment, within 7 working days of the referral date. Eligibility rate will be calculated for each of the 4-week time periods and reported for the entire study duration of 12 weeks. It will be entered as a binomial variable at the student level indicating if referred student is "eligible" to receive counselling.	Adolescent reported SDQ					
Self-referral rate	Self-referral rate is defined as the proportion of referrals which are self-initiated as a function of the number of referred adolescents in a given condition. Self-referral rate will be calculated for each of the 4-week time periods and reported for the entire study duration of 12 weeks, based on data from	Referral logs					

Table 1 Primary, secondary and exploratory outcomes for the sensitization trial

Outcome	Explanation	Measures/ Source
	researchers' referral logs. It will be entered as a binomial variable at the student level indicating if the referral was a self-referral.	
EXPLORATORY	OUTCOMES	
Severity of mental health symptoms	The SDQ total difficulties score will be used to assess the severity of mental health symptoms. It is calculated by adding the scores of all the SDQ sub-scales except the pro-social scale.	Adolescent reported SDQ
Severity of symptom types	Internalizing and externalizing symptom subtypes will be assessed as an exploratory outcome for the students referred across the control and intervention conditions. Externalising score is calculated as the sum of the conduct and hyperactivity scales (ranges from 0 to 20). Internalising score is calculated as the sum of the emotional and peer problems scales (ranges from 0 to 20).	Adolescent reported SDQ

3.1 Trial Design

The trial will be implemented as a Stepped Wedge Cluster Randomised Controlled Trial (SW-CRCT). The essential feature of a SW-CRCT is that random allocation determines the time period in which clusters begin an intervention. All clusters start with the first time period of control intervention, and cross-over from the control to the intervention condition across pre-defined time periods, in a random, but sequential, order(4).

We will select 70 classes using stratified randomisation to represent each of the grades 9th, 10th, 11th, 12th across the six participating schools in Delhi with probability proportional to size.

		Step 1	Step 2	Sequence of receiving treatments*
Sequence 1 (1-35 classes)	Control condition	Intervention condition	Intervention condition	011
Sequence 2 (36-70 classes)	Control condition	Control condition	Intervention condition	001
Time	1 st time period (4 weeks)	2 nd time period (4 weeks)	3 rd time period (4 weeks)	

Figure 1: Illustration showing implementation of the control and intervention conditions.

Notes: The white boxes indicate the group of classes in the control condition and the coloured boxes indicate the group of classes in the intervention condition. *0=control condition; 1=intervention condition The 70 classes will be randomised to be a part of either of 2 sequences as shown in Figure 1. A small block size of 2 will be used to allocate the 70 classes across the two sequences in order to ensure balance, as the number of classes within each grade from the individual schools is relatively small. In the rare instance that a selected class has been dissolved or merged with another class, the next class in the random list will be included to replace the unavailable class. Each sequence will be implemented over three consecutive 4-week intervals. The trial will be conducted over 12 weeks except for breaks due to exams and holidays. All classes will begin with the control intervention period of 4 weeks, where only school level activities will be rolled out.

Notes: The white boxes indicate the group of classes in the control condition and the coloured boxes indicate the group of classes in the intervention condition.

3.2 Study setting

The trial will be conducted in six Government-run secondary schools in New Delhi, India. The schools were purposively selected in consultation with the Department of Education, Government of New Delhi, to focus on relatively under-served, low-income communities. Of the six schools, three are boys' schools, two are girls' schools and one is co-educational. As of August 2018, there were 172 classes in grades $9^{th} - 12^{th}$ with a total student population of 8448 (ranging from 1050 to 1632 per school; mean=1408, SD=225), including 4694 (56%) boys and 3754 (44%) girls.

3.3 Eligibility criteria

CLASSES (CLUSTERS)

Inclusion criteria:

• Classes from grades 9th – 12th in the six collaborating schools.

Exclusion criteria:

• Classes that have received classroom sensitization sessions during earlier pilot work.

ADOLESCENT PARTICIPANTS

Inclusion criteria:

- Enrolled as a student in grades 9th 12th (aged 13-20 years) at one of the collaborating schools
- Adolescent willing and able to consent for participation in the research Exclusion criteria:
- Adolescent not proficient in written and spoken Hindi, as needed to participate fully in study procedures
- Adolescent needing urgent medical or mental health care

3.4 Interventions

Intervention condition. This will comprise a one-off 30-minute classroom session that is intended to improve understanding about signs and symptoms of mental health problems, raise awareness about the school counselling service, and generate demand for the service. The session will be delivered for individual classes (approximately 50 students per class) by a counsellor (drawn from the same group responsible for the problem-solving intervention in the host trial) with assistance from a researcher who has additional responsibilities for processing referrals and conducting eligibility assessments. The classroom session will start with a short animated video (link to video) which provides age-appropriate information about types, causes, impacts and ways of coping with common mental health problems. The video is followed by a guided group discussion, structured around a standardized script that builds on the topics covered in the video. In case of technical difficulties that may prevent the video from being shown, the counsellor will use a flipchart based on printed images from the video. At the end of the session, students will be handed a self-referral form which includes normalizing information and question-based prompts to assist with self-identification of mental health problems. Interested students can approach the facilitators immediately after the session with self-referral forms, or else deposit the forms discreetly in a secure drop-box located outside or near to the counsellor's usual room.

The counsellors and researchers delivering the classroom sensitization sessions will be provided with a structured manual and complete a one-day office-based training. Training will be conducted by master's level psychologists (who will also serve as supervisors) and comprise lectures, demonstrations and role-plays. The training will be followed by a period of supervised field practice, when the counsellors and researchers will be required to complete at least two classroom sessions independently under direct observation from supervisors. Fidelity of intervention delivery will be assessed on a checklist of observable procedures which have been distilled from the intervention manual. Each procedure will be rated on a three-point Likert scale (not completed, partially completed, fully completed). A 'refresher' training session will also be conducted before the trial begins.

Control condition. This will comprise whole-school sensitization activities. The supervisor will meet the principal of each school individually to inform them about planned counselling and research activities and to seek their cooperation for the same. This meeting will also provide structured information about common mental health problems faced by adolescents, and address any concerns related to planned procedures and resource demands. Teachers will be invited to participate in separate group sensitization meetings (up to 30 teachers at a time). A standardized script will mirror the topics covered in the meetings with the school principals, but with additional emphasis placed on referral procedures for the host trial. Up to three meetings will be held in each school to maximize coverage of teaching staff. The meeting will be conducted by the same counsellor and researcher pairing responsible for delivering the classroom intervention. Posters will be placed in highly visible locations such as noticeboards or common corridors, in addition to signage on the drop-box, which will remind students (and teachers) of the counselling service.

Across both the conditions, students deemed ineligible for participation in the host trial will be allowed to re-refer themselves after a gap of 4 weeks, offering a suitable time period to re-assess mental health status in line with the host trial's inclusion criterion about symptom chronicity.

3.5 Measures

Strengths and Difficulties Questionnaire (SDQ):

The SDQ is a 25-item self-report measure of youth mental health difficulties(2). A Total Difficulties score is derived by summing items from four problem subscales (Emotional, Conduct, Hyperactivity/inattention, and Peer relationship), while a fifth subscale measures prosocial functioning and does not contribute to the overall severity score. Individual problem scale items are scored from 0-2 (with higher scores indicating greater problem severity), giving a range of 0-40 for Total Difficulties.

The SDQ has been validated in more than 80 languages (including Hindi and other Indian languages) and used in over 100 countries, making it the most widely used clinical and research instrument in the field of child and adolescent mental health globally. It has been applied in a number of surveys and as an outcome measure in trials with school-going adolescents in India(5-8). Singh et al, 2015(7) reported acceptable internal consistency for the adolescent-reported Total Difficulties Score (English version, Cronbach's alpha=0.62; Hindi version, Cronbach's alpha=0.61). In pilot work leading up to the current trial, the SDQ was administered to 48 adolescents from secondary schools in New Delhi, demonstrating acceptable internal consistency for the Total Difficulties Score (Cronbach's alpha=0.63)

Eligibility for the PRIDE counselling service/host trial will be determined by a score in the borderline or abnormal range adapted for the Indian sample (\geq 19 for boys and \geq 20 for girls) on the SDQ Total Difficulties Score(9), as well as scoring in the abnormal range (\geq 2) on the Impact Supplement(2). To ensure that participants are experiencing persistent and disabling difficulties rather than transient distress/impairment, the SDQ Chronicity item will be used to confirm the presence of self-reported mental health difficulties for 1 month or longer.

For describing the symptom types, we will use the broader sub-scales for internalising and externalising symptoms that are calculated by adding scores of specific sub-scales. The use of these broader sub-scales is preferred over individual sub-scale score in general population(3). For calculating externalising symptoms score, we will add scores of the conduct and hyperactivity scales. The range of the externalising sub-scale score is 0 to 20. Similarly, for calculating internalising symptoms score, we will add scores of the score of internalising sub-scale score in general population (3).

3.6 Power calculation

We based our power calculation on a within-period comparison for a stepped wedge design(10), using Stata package "clustersampsi". Based on pilot data, we anticipated referral rates of 5% and 15% on the control and intervention conditions respectively, with an intra-cluster correlation coefficient (ICC) of 0.124. We assumed the same ICC for the between-time correlation given the short time period of follow-up. In practice, it may be smaller than 0.124 and both ICCs will be reported. Using these parameters, a sample size of 70 classes (average class size of 50 students) will have 92% power to detect a difference of 10 percentage points (treating the outcome as a binomial variable), at a significance level of 0.05.

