6.4 Sensitivity analysis

The sensitivity analyses is based on the methods described in Thompson et al, 2018 (10) which is also used for calculating the power of the study. It uses data from the 2nd period only, since it is in this period where the two conditions differ most transparently: sensitization intervention versus no sensitization intervention. We will use GEE method to arrive at population averaged estimates of the effects of exposure to the interventions across the control and intervention conditions. As the power calculation for this trial is based on this method, we will assess the robustness of the results obtained by the primary method of analysis using this method.

To estimate the intervention effect, we need to estimate the parameters in the following regression equation

$$logit(P(Y_{ijkl})) = \mu + \theta X_i$$

where Y_{ijkl} is as before, μ is a constant, θ is the parameter of interest (the population-averaged estimate of the effect of the intervention), X_i is in indicator variable ($X_i = 0$ for the control condition and $X_i = 1$ for the intervention condition).

A separate file with a sub-set of data with all observations pertaining to time period 2 will be created for the analysis. Having data with one record for each student, and a variable to indicate the class in which the observations are nested (class_id), an indicator for being assigned to the intervention condition (intervention) and an indicator for the outcome variable of being referred (referred), the following stata commands will be used to analyse the intervention effect in period 2. We will first specify the panel data structure with clustering of data at class level using the command "xtset" and then specify the GEE model through the stata command "xtgee".

"xtset class_id"

STATISTICAL ANALYSIS PLAN FOR THE SENSITIZATION TRIAL

"xtgee referred intervention, family(binomial) link(logit) corr(independent) vce(robust)"

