6.6 Other analysis

The intracluster correlation coefficient will be calculated and its impact on the assumed power of the trial will be assessed post-hoc.

7. Ethical considerations

Ethical approval has been obtained from the ethics committees of Sangath, Goa (Ref:RP_2018_47), and Harvard Medical School (Ref:MOD17-0379-03). The trial is registered prospectively on ClinicalTrials.gov and identified through protocol number NCT03633916 (available at: https://clinicaltrials.gov/ct2/show/NCT03633916).

References

1. Parikh R, Michelson D, Malik K, Shinde S, Weiss HA, Hoogendoorn A, et al. The effectiveness of a low-intensity problem-solving intervention for common adolescent mental health problems in New Delhi, India: protocol for a school-based, individually randomized controlled treatment trial with an embedded stepped-wedge cluster randomized controlled recruitment trial. Trials. submitted.

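### Is the 92% power in section 3.6 wrong, given that the usual formula gives about 96% from the listed inputs?

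*SAP*

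**What the plan says.** Section 3.6 bases power on a comparison within one period, run in the Stata package clustersampsi. From pilot data, "we anticipated referral rates of 5% and 15% on the control and intervention conditions respectively", with "an intra-cluster correlation coefficient (ICC) of 0.124". It continues: "Using these parameters, a sample size of 70 classes (average class size of 50 students"), at a significance level of 0.05, "will have 92% power to detect a difference of 10 percentage points".

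Three other sections bear on the figure:

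- Section 3.1: "A small block size of 2 will be used to allocate the 70 classes across the two sequences", which gives 35 classes in each.
- Section 6.4: the sensitivity analysis uses the second period only. "As the power calculation for this trial is based on this method", the figure refers to 35 intervention against 35 control classes in that period.
- Section 6.6: the ICC will be calculated from the trial data and "its impact on the assumed power of the trial will be assessed post-hoc".

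Section 3.6 does not state whether the test is one- or two-sided, how much class size varies, or which formula or program option was chosen.

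**The concern.** Section 3.6 presents 92% as the direct output of its list of inputs. A reader who puts that list into the usual formula gets about 96%. A gap of 4 points is too large for rounding, so either the figure is wrong or something behind it is not written down.

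Two things could be at stake. The first is whether the trial is large enough. The second is the check in section 6.6, which needs a planned figure that can be recomputed. By the usual formula, an observed ICC of 0.16 gives 92.0%. Set beside the stated 92%, a rise of 29% in the ICC (0.16/0.124 = 1.29) would seem to cost no power.

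**Working it through.** **Inputs.** From section 3.6: rates 0.05 and 0.15, ICC 0.124, 50 students per class, significance level 0.05. From sections 3.1 and 6.4: 35 against 35 classes. Assumed: two-sided test, critical value 1.96.

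**Usual formula (equal classes, the same ICC in both arms).**

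- Design effect = 1 + 49 × 0.124 = 7.076
- Effective students per arm = 35 × 50 / 7.076 = 247.3
- Binomial variances: 0.05 × 0.95 + 0.15 × 0.85 = 0.0475 + 0.1275 = 0.175
- Standard error = √(0.175 / 247.3) = 0.0266
- 0.10 / 0.0266 = 3.76; 3.76 − 1.96 = 1.80; power = 96.4%

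This does not reproduce 92%. Nor do the close variants:

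| Variant | Power |
|---|---|
| Pooled variance under the null | 96.2% |
| Unpooled, t with 68 degrees of freedom | 95.9% |
| Continuity-corrected (pooled) | 94.7% |
| Log-odds scale | 94.3% |
| Log-odds scale, t with 68 degrees of freedom | 93.6% |
| One-sided 0.05, unpooled | 98.3% |

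The actual mean class size does not explain the gap. Section 3.2 reports 172 classes "with a total student population of 8448", so the mean is 8448 / 172 = 49.1, and power stays at 96.1% to 96.4%.

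**Route 1 to 92%: between-class variation proportional to the rate.** The ICC is converted to a between-class coefficient of variation *k* at the mean rate of 0.10:

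- *k*² = 0.124 × 0.90 / 0.10 = 1.116
- Variance per pair of classes = 0.175 / 50 + 1.116 × (0.05² + 0.15²) = 0.0035 + 0.0279 = 0.0314
- √(35 × 0.10² / 0.0314) = √11.15 = 3.339; 3.339 − 1.96 = 1.379; power = 91.6%
- With the factor 1 − 1/50 on the *k*² term, the variance is 0.03084 and power is 92.1%

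Both round to 92%, and neither needs an input beyond those listed. The result depends heavily on the rate used for the conversion: at 5% power is about 66%, and at 15% about 98%.

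**Route 2 to 92%: unequal class sizes.** With a coefficient of variation CV of class size, the design effect is 1 + ((1 + CV²) × 50 − 1) × 0.124.

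- At CV = 0.5: 1 + 61.5 × 0.124 = 8.626; effective n = 1750 / 8.626 = 202.9; power 92.2% (pooled) or 92.6% (unpooled)
- CV that gives 92.0%: 0.51 (pooled), 0.53 (unpooled), 0.37 (continuity-corrected), 0.35 (log-odds)

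**The section 6.6 comparison.** By the unpooled formula with equal classes, an ICC of 0.16 gives 92.0%. That hides a loss only if the planned and the observed figure come from different formulas. Repeating one calculation at both values shows the loss:

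- Usual formula: 96.4% falls to 92.0%.
- Route 1: *k*² = 0.16 × 9 = 1.44; variance = 0.0035 + 1.44 × 0.025 = 0.0395; √(0.35 / 0.0395) = 2.977; 2.977 − 1.96 = 1.017; 91.6% falls to 84.5%.
- Route 2 (CV 0.5, pooled): design effect = 1 + 61.5 × 0.16 = 10.84; effective n = 1750 / 10.84 = 161.4; 92.2% falls to 85.3%.

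**The case for a change.** The strongest case for asking for a change is that the text ties 92% to its own list and frames the target as a difference in percentage points for a binomial outcome. The natural reading is the risk-difference formula, and that gives about 96%. Simulation of the period-2 analysis (independence GEE, logit link, robust standard errors) with equal classes agrees, at 96.0% to 96.1%. Neither route to 92% is stated. One sentence naming the option would cost almost nothing and would let anyone repeat the section 6.6 check on the same basis.

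The arithmetic in this stands, and so does the observation that section 3.6 is under-documented. Two parts do not stand. First, it does not follow that 92% is an error. Route 1 reaches it from the listed inputs, and the simulation cannot rule that route out because it builds in the same ICC in both arms, which is the assumption in question. Section 3.6 also speaks of an average class size, which leaves room for varying sizes. Second, the harm in section 6.6 needs a switch of formula that the SAP does not describe. The team holds its own calculation and would repeat it with the observed ICC. That check decides nothing in the analysis.

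Replacing 92% with 96% could also do damage: it would put a more optimistic figure, resting on equal classes and a common ICC, in place of one that a recognised formula reproduces. A request to say that the figure concerns period 2 adds nothing, because sections 3.6 and 6.4 together already say so.

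**Conclusion.** No change is needed. The usual formula gives 96.2% to 96.4% and its common variants about 94% to 96%, so 92% cannot be read straight off the list in section 3.6. It is nevertheless within reach of a recognised formula using only those inputs (91.6% to 92.1%), or of a class-size CV of about 0.35 to 0.53. Which of these the authors used, if either, cannot be told from the SAP.

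The gap is one of documentation. Against the usual formula the stated figure is about 4 points too low, so nothing suggests that 70 classes are too few on the stated assumptions. The number of classes, the allocation, the analyses in sections 6.2 and 6.4 and the inference stay as they are. An analyst doing the section 6.6 check fills the gap by computing planned and observed power in the same way.

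These conclusions assume a two-sided 0.05 test and 35 against 35 classes averaging 50. The Route 1 result also assumes conversion of the ICC at 10%, to which it is sensitive.
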